### 11.3.2 Guidelines for reporting serious adverse events

In the case of a SAE, the Investigator must immediately:

- ENTER (within 24 hours) the information related to the SAE in the appropriate screens of the eCRF; the system will automatically send the notification to the monitoring team after approval by the Investigator within the eCRF or after a standard delay.
- SEND (preferably by fax or e-mail) the photocopy of all examinations carried out and the dates on which these examinations were performed, to the representative of the monitoring team whose name, fax number, and e-mail address appear on the clinical trial protocol. Care should be taken to ensure that the subject's identity is protected and the subject's identifiers in the clinical trial are properly mentioned on any copy of source document provided to the Sponsor. For laboratory results, include the laboratory normal ranges.
- All further data updates should be recorded in the eCRF as appropriate, and further documentation as well as additional information (for laboratory data, concomitant medication, subject status, etc.) should be sent (by fax or e-mail) to the monitoring team within 24 hours of knowledge. In addition, any effort should be made to further document within the week (7 days) following initial notification any SAE that is fatal or life threatening.
- A back-up plan is used (using paper flow) when the eCRF system does not work.

#### Back-up plan

- SEND (within 24 hours, preferably by fax or e-mail) the signed and dated corresponding page(s) in the case report form to the representative of the monitoring team whose name, fax number, and e-mail address appear on the clinical trial protocol.
- ATTACH the photocopy of all examinations carried out and the dates on which these examinations were performed. Care should be taken to ensure that the subject's identity is protected and the subject's identifiers in the clinical trial are properly mentioned on any copy of source document provided to the Sponsor. For laboratory results, include the laboratory normal ranges.
- All further documentation should be sent to the monitoring team within 24 hours of knowledge. In addition, every effort should be made to further document within the week (7 days) following initial notification any SAE that is fatal or life threatening.

Any SAE brought to the attention of the Investigator at any time after the end of the study for the subject and considered by the Investigator to be caused by the IMP with a reasonable possibility, should be reported to the monitoring team.

### 11.3.3 Guidelines for reporting adverse events of special interest

For AESI, the Sponsor is to be informed immediately (ie, within 24 hours), as per SAE notification guidelines described in [Section 11.3.2](#), even if a seriousness criterion is not met, using the corresponding pages of the case report form (to be sent) or screens in the eCRF.

### 11.3.4 Guidelines for reporting events of special interest

If an EOSI fulfills the criteria of an SAE, reporting should be performed according to the instructions for reporting of SAEs (see [Section 11.3.2](#)). Otherwise, reporting should follow the instructions for an AE (see [Section 11.3.1](#)).

### 11.3.5 Guidelines for management of specific laboratory abnormalities

Once the subject is included in the clinical trial, the following laboratory abnormalities must be monitored, documented, and managed according to the related decision charts in [Appendix B](#).

- Neutropenia
- Thrombocytopenia
- ALT increase
- Creatine phosphokinase (CPK) increase, suspected to be on non-cardiac origin and not related to an intensive physical activity

Renal function and the extent of renal injury that is commonly precipitated by intensive diuretic treatment in this patient population will be reviewed on a frequent basis by an independent renal expert, member of the Data Monitoring Committee (DMC), who shall communicate potential issues to the Sponsor. Overall renal safety in Cohorts 1 and 2 will be assessed by the DMC.

## 11.4 OBLIGATIONS OF THE SPONSOR

During the course of the study, the Sponsor will report in an expedited manner:

- All SAEs that are both unexpected and at least reasonably related to the IMP (SUSAR), to the Regulatory Authorities, IRB/IECs as appropriate and to the Investigators.
- All SAEs that are expected and at least reasonably related to the IMPs to the Regulatory Authorities, according to local regulations.
- The following AESI to the Regulatory Authorities requiring such reporting:
  - Pregnancy
  - Symptomatic overdose
  - ALT increase >3 x ULN

Adverse events that are considered as expected events will be specified by the reference safety information provided in the Investigator's Brochure.

If required, unblinding of SUSARs will be the responsibility of the Sponsor.

The Sponsor will report all safety observations made during the conduct of the trial in the clinical study report.

## **11.5 SAFETY INSTRUCTIONS FOR DIABETIC COMPLICATIONS**

### **11.5.1 Hypoglycemia**

During the study, diabetic patients are instructed to document any hypoglycemic episodes in their study diary. The hypoglycemia will be reported in the specific e-CRF page with onset date and time, symptoms and/or signs, the SMBG value if available, and the treatment. Unless the event fulfills SAE criteria, hypoglycemia will not be reported as an AE.

Hypoglycemia is categorized according to the ADA workgroup on hypoglycemia classification (25) and summarized in [Figure 1](#).

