
PRIMARY ENDPOINT(S) AND MAIN SECONDARY ENDPOINT(S)
	
Primary endpoints:  Safety and Toxicity:        Safety assessment include:        AEs, hypoglycemia (all investigator reported events, severe and/or documented symptomatic or asymptomatic), Events of Special Interest (EOSIs), Adverse Events of Special Interest (AESIs), AEs leading to discontinuation from the IMP, serious AEs (SAEs), and deaths.        Clinical laboratory results        Vital signs and electrocardiogram (ECG) results.
 
Pharmacodynamics:        Changes in hemococoncentration from baseline to 14 days.        Changes in plasma volume from baseline to 14 days.
 
Secondary endpoints:        Change in erythropoietin from baseline to 14 days        Change in NT-proBNP from baseline to 14 days
 
Other endpoints:        Change in total body water from baseline to 14 days        Change in uric acid from baseline to 14 days        Change in beta-hydroxybutyrate from baseline to 14 days        Change in total blood volume from baseline to 14 days

	
Change in red cell mass from baseline to 14 days
 
Percentage of patients with <math>\geq 15\%</math> of deaerated volume on study day 14
 
Blood pressure, sitting (SBP and DBP) at day 14 compared to baseline

ASSESSMENT SCHEDULE	
Screening will occur when patients are hospitalized or had urgent visit to emergency department or heart failure unit/coronary care center and treated with intravenous diuretics for worsening heart failure. Randomization (Day1) will take place within 7 days following discontinuation of intravenous treatment with diuretics.
 
Baseline laboratory parameters, total body water and plasma volume measurements, initiation of IMP administration occur on Day 1.
 
The final assessment for hemoconcentration, total body water and plasma volume changes will be on day 14<math>\pm</math>1 day.

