### 10.2 SAFETY

Assessments for safety include AEs, clinical laboratory assessments, physical examination, ECG, weight and vital signs. An independent DMC will meet on a regular basis to review accumulating clinical trial safety data. Enrollment in Cohort 2 will only proceed following review of cases in Cohort 1 by the DMC, and similarly enrollment in Cohort 3 will only proceed following review of cases in Cohort 2 by the DMC.

Serum creatinine will be assessed at Baseline (Day 1, Visit 1) and on-site Visits 2, 3 and 4 (in cohort 3 on-site visit 4 was eliminated precluding any serum collection). A central laboratory will analyze samples and estimate change from Baseline in serum creatinine and eGFR. Renal safety will also be assessed on a regular basis by an independent expert, who may also be a member of the DMC.

The following safety endpoints will be assessed:

- Adverse events, AEs leading to discontinuation from the IMP, adverse events of special interest (AESIs), Events of Special Interest (EOSIs), SAEs and deaths
- Hypoglycemia (severe, documented symptomatic, or asymptomatic)
- Clinical laboratory results, vital signs and ECG results

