#### 11.2.4 Events of Special Interest (EOSIs)

An EOSI is a serious or non-serious AE of scientific and medical concern specific to the Sponsor’s product or program, for which ongoing monitoring may be appropriate. Such events may require further investigation in order to characterize and understand them. These events should be reported on the specific e-CRF page and will only qualify for expedited reporting when serious (fulfilling SAE criteria).

The EOSIs for this study are:

4. MACE (cardiovascular death, myocardial infarction, or stroke) and other specific CV events (eg, heart failure leading to hospitalization).
5. Severe hypoglycemia (see [Section 11.5.1.1](#))
6. Venous thrombotic events (including venous thrombosis deep and pulmonary embolism)
7. Pancreatitis
8. Fracture bone
9. AEs leading to amputations
10. Diabetic Ketoacidosis (DKA)
11. Malignancies of special interest (breast, bladder, renal cell, Leydig cell tumor of the testis, pancreatic, prostate, and follicular thyroid cancer)
12. Genital mycotic infections (to include vulvovaginal candidiasis in females and candida balanitis in males)
13. Urinary tract infection
14. Diarrhea

15. Volume depletion with serious consequence (orthostatic hypotension, orthostatic collapse fall, fracture)
16. Renal events, to include 50% decline in eGFR, end stage renal failure, renal death defined as eGFR < 15 ml/min/1.73m^2

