2.7.1.2 Treatment-emergent adverse events

The following TEAEs summaries will be provided by treatment for the safety population:

- Overview of TEAEs: number and percentage of patients with any TEAE, any TEAE of special interest, any severe TEAEs, any serious TEAE, any TEAE leading to death (if any occurred), and any TEAE leading to permanent treatment discontinuation.
- Summary of TEAEs by primary SOC and PT:
 - number and percentage of patients with at least one TEAE;
 - number of occurrences of TEAEs.

Patients presenting TEAEs will be listed sorted by treatment group primary SOC and PT.

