Albumin		
Low (adults)	\leq 25 g/L	
Creatine Kinase		
High, all grades	> 3 ULN	\geq 3 ULN
At least grade 1 (adults)	> 3 ULN	
At least grade 2 (adults)	> 10 ULN	
Sodium		
Low	\leq 129 mmol/L	\leq 129 mmol/L
High	\geq 160 mmol/L	\geq 150 mmol/L
Potassium		
Low	< 3 mmol/L	Birth/0 to 27 days old : \leq 3.0 mmol/L 28 days/1 month to 16/18 years old : \leq 3.5 mmol/L
High	\geq 5.5 mmol/L	Birth/0 to 27 days old : \geq 7.0 mmol/L 28 days/1 month to 23 months old : \geq 6.0 mmol/L 24 months/2 years to 16/18 years old : \geq 5.5 mmol/L
Creatinine		
High	\geq 150 μ mol/L	Birth/0 to <6 years old : >53 μ mol/L 6 years to <12 years old: >90 μ mol/L 12 years to 16/18 years old: >132 μ mol/L

Laboratory parameter	Adults	Children
PCSA criteria n/N1 (%)		
Increase from baseline		
At least grade 1 (adults)	≥ 30% change from baseline	
At least grade 2 (adults)	≥ 100% change from baseline	
Creatinine Clearance		
Low, all grades	< 90 mL/min*	Birth/0 to 27 days old : < 25 ml/min/1.73m ² ** 28 days/1 month to 23 months old: < 45 ml/min/1.73m ² ** From 2 years old : < 60 ml/min/1.73m ² **
Mild (adults)	[60 – 90[mL/min*	
Moderate (adults)	[30 – 60[mL/min*	
Severe (adults)	[15 – 30[mL/min*	
End stage (adults)	< 15 mL/min*	
*MDRD or Cockcroft-Gault equation		**GFR Bedside Schwartz Formula Based on normal ranges: 20 to 50 (<8 days), 25 to 80 (8 days to 1 month), 30 to 90 (1-6 months), 40 to 115 (6-12 months), 60 to 190 (12-23 months), 90 to 165 (2-12 years), 80-120 (After 12 years)
BUN		
High	≥ 17 mmol/L	Birth/0 to 27 days old : ≥4.3 mmol/L 28 days/1 month to 16/18 years old: ≥6.4 mmol/L
Alanine Aminotransferase		
High, at least grade 1	> 3 ULN	≥ 3 ULN
High, at least grade 2	> 5 ULN	≥ 5 ULN
High, at least grade 3	> 10 ULN	≥ 10 ULN
High, at least grade 4	> 20 ULN	≥ 20 ULN
Aspartate Aminotransferase		
High, at least grade 1	> 3 ULN	≥ 3 ULN
High, at least grade 2	> 5 ULN	≥ 5 ULN
High, at least grade 3	> 10 ULN	≥ 10 ULN
High, at least grade 4	> 20 ULN	≥ 20 ULN

Laboratory parameter	Adults	Children
PCSA criteria n/N1 (%)		
Alkaline phosphatase		
High	> 1.5 ULN	≥ 1.5 ULN
Total Bilirubin		
High, all grades	> 1.5 ULN	≥ 1.3 ULN
At least grade 1 (adults)	> 1.5 ULN	
At least grade 2 (adults)	> 2 ULN	
Alanine Aminotransferase and tot bilirubin		
High	ALT > 3 ULN and TBILI > 2 ULN	ALT ≥ 3 ULN and TBILI ≥ 2 ULN
Direct bilirubin and total bilirubin		
High	BILDIR >35% TBILI and TBILI >1.5 ULN	BILDIR >35% TBILI and TBILI ≥ 1.3 ULN

References:

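### Hypoglycemia and events of special interest are primary safety endpoints, but the SAP plans no hypoglycemia summary and no event-of-special-interest grouping, and the protocol gives conflicting AE rules for severe, non-serious hypoglycemia

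*Protocol*

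**What the plan says.** The primary endpoints in the protocol's trial summary include "hypoglycemia (all investigator reported events, severe and/or documented symptomatic or asymptomatic), Events of Special Interest (EOSIs") alongside AEs, AESIs, AEs leading to discontinuation, serious AEs and deaths. Protocol 10.2 repeats this. One bullet groups AEs with "adverse events of special interest (AESIs), Events of Special Interest (EOSIs), SAEs and deaths", and a separate bullet reads "Hypoglycemia (severe, documented symptomatic, or asymptomatic").

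Protocol 11.5.1 has hypoglycemia recorded on a dedicated e-CRF page with time, symptoms, glucose value where available and treatment. It adds: "Unless the event fulfills SAE criteria, hypoglycemia will not be reported as an AE".

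Protocol 11.2.4 defines an EOSI as an AE, serious or not, and lists severe hypoglycemia as item 5. For an EOSI that is not serious, Protocol 11.3.4 says: "Otherwise, reporting should follow the instructions for an AE".

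The TEAE overview in SAP 2.7.1.2 gives, by treatment, the "number and percentage of patients with any TEAE, any TEAE of special interest, any severe TEAEs, any serious TEAE", with further entries for death and permanent discontinuation. SAP 2.7.1.5 limits the special-interest table to AESIs, namely pregnancy, symptomatic overdose and ALT increase. The SAP has no EOSI output, and the abbreviation is missing from its list.

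**The concern.** The primary objective is safety and tolerability compared with placebo. An endpoint named under that objective needs a planned comparison by arm, at least a descriptive one. Non-serious hypoglycemia is outside the AE data by rule, so the TEAE tables cannot contain it, and no other table is specified to take it. For a drug that lowers blood glucose, a reader of the study report would look for that table first.

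The two reporting rules for severe hypoglycemia raise a second problem. If sites resolve the conflict differently, the TEAE count depends partly on site practice as well as on what happened to patients.

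**Working it through.** The plan gives no figure to reproduce, and the check is a comparison of text with a simple count.

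**1. Primary safety items matched to planned outputs.** The trial summary names seven event-type items.

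| Item | Planned output | By-arm summary? |
|---|---|---|
| AEs | SAP 2.7.1.2 overview; table by organ class and preferred term | Yes |
| AESIs | SAP 2.7.1.2 overview; SAP 2.7.1.5 table | Yes |
| AEs leading to discontinuation | SAP 2.7.1.2 overview; listing in 2.7.1.4 | Yes |
| Serious AEs | SAP 2.7.1.2 overview; listing in 2.7.1.3 | Yes |
| Deaths | SAP 2.7.1.2 overview; listing in 2.7.1.3 | Yes |
| Hypoglycemia | None specified | No |
| EOSIs | None specified as a group | Preferred terms only |

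Five of seven have a dedicated output and two do not. Protocol 14.8.1.5 does not fill the gap, because it too tabulates only AESIs.

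**2. Path of a non-serious hypoglycemia.** It goes to the hypoglycemia e-CRF page and, under Protocol 11.5.1, not to the AE page. It therefore cannot enter the TEAE overview or the preferred-term table. Two outputs remain:
- the individual data listings in SAP 2.9, which are not counts with denominators;
- the count of low laboratory glucose in SAP 2.7.2 and Appendix C (at or below 3.9 mmol/L and below the lower limit of normal).

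The second flags a laboratory value. Protocol 10.2.1 takes laboratory blood samples fasting, and in cohort 3 the flow chart has biochemistry after Day 1 only at Visits 3 and 5. It cannot represent symptomatic, assisted or self-measured episodes at home.

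**3. Path of a severe, non-serious hypoglycemia.** Protocol 11.5.1.1 calls an event severe when another person must give help, and expressly requires SAE reporting when there is unconsciousness, coma or seizure. Take an assisted event with none of these that meets no other seriousness criterion:
- Protocol 11.2.4 (item 5) with 11.3.4: report as an AE.
- Protocol 11.5.1: do not report as an AE.

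The same event adds one to the TEAE count under the first rule and nothing under the second.

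**4. Path of the other EOSIs.** They are AEs by definition, so they reach the SAP 2.7.1.2 table by arm, with patients and occurrences. Urinary tract infection, diarrhea, pancreatitis and ketoacidosis would be visible as terms. Renal change is also covered by the creatinine criteria (rises of at least 30% and at least 100%), the clearance classes and the descriptive eGFR output (SAP 2.7.2, 2.7.5, Appendix C). Volume effects are covered in part by orthostatic and low blood pressure outputs (SAP 2.7.3, Appendix C). What is missing is the category total. Composite categories such as MACE or volume depletion with serious consequence spread over several terms. Patient counts for those terms cannot be added, because one patient may appear under more than one.

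**5. EOSI 16.** The item lists a 50% eGFR decline, end stage renal failure, and "renal death defined as eGFR < 15" mL/min/1.73m². Read literally, a living patient with that eGFR would be a renal death. SAP Appendix C labels clearance below 15 mL/min "End stage (adults"). The units differ, so these are not strictly the same quantity, but the labels point different ways.

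**The case against.** The strongest reply is that hypoglycemia is handled separately by design. Protocol 10.2 lists it apart from AEs, a dedicated page captures it, events with unconsciousness, coma or seizure are SAEs and so enter the TEAE tables, individual data are listed by treatment group, and Protocol 11.4 commits the sponsor to reporting all safety observations in the study report. The trial is exploratory, its safety analysis is descriptive, and an independent DMC reviews safety data. All of this stands, and it makes the matter one of analysis, not of lost data. It does not supply a by-arm summary of a named primary safety endpoint.

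A second reply is that the reporting conflict is narrow. It is confined to severe hypoglycemia meeting no seriousness criterion, and the medically-important clause in Protocol 11.2.2 may capture some of those events. That also stands.

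Third, SAP 1.5 refers to an outside standard for analyses, which may contain such tables. It cannot be checked here. The SAP says its purpose is prespecification, so the table belongs in the SAP itself.

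Fourth, the SAP was written to the protocol as amended in March 2018. The change table for Amendment 03 lists nothing on hypoglycemia or EOSIs, so the SAP's age does not explain the omission.

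**Conclusion.** The gap is real and moderate in size. Two of seven event-type primary safety items have no dedicated by-arm output, and one class of event has two opposite reporting rules. This assumes that neither the outside standard cited in SAP 1.5 nor SAP text unavailable here adds these outputs.

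The documents do not support some stronger readings that a reader might infer:
- That all 13 EOSI categories (items 4 to 16) lack any by-arm summary, or that renal, volume, ketoacidosis and infection events would never be compared by arm. Preferred-term tables and the laboratory, eGFR and blood pressure outputs cover much of this; only the grouping is absent.
- That the safety report must understate hypoglycemia. The episodes are recorded in a separate stream that has no planned summary.
- That about 19 of 64 patients are diabetic. The 30% minimum is in SAP 1.3, in a section sized for 81 patients (0.30 × 81 = 24.3). The 64 comes from the amended protocol, which states no such minimum. Applying one to the other (0.30 × 64 = 19.2) mixes two designs.
- That EOSI 16 will misclassify deaths in a planned table. No EOSI table is planned; the wording needs clarifying before one is added.

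**What to change.** Before database lock, add two tables to SAP 2.7.1, by treatment group, within the SAP's TEAE period:
1. Hypoglycemia from the dedicated e-CRF page: patients (n, %) and events for any hypoglycemia and for the severe, documented symptomatic and asymptomatic classes, overall and in diabetic patients. The any-hypoglycemia row covers the probable and relative classes; separate rows for them are optional.
2. EOSIs by category and preferred term: patients (n, %) and events.

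Reconcile Protocol 11.2.4 and 11.3.4 with 11.5.1, so that severe but non-serious hypoglycemia is counted the same way at every site. State in the SAP which dataset feeds which table, so that an event recorded on both pages is not counted twice within a table.

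Ask the sponsor to clarify what the eGFR threshold in EOSI 16 defines, and how it relates to the class in SAP Appendix C.

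The cost is two tables from data already collected, one protocol clarification on reporting and one wording query. No new assessment or patient visit is needed.

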#### **11.5.1.1 Severe hypoglycemia**

Severe hypoglycemia is an event requiring assistance of another person to actively administer carbohydrate, glucagon, intravenous glucose or other resuscitative actions. These episodes may be associated with sufficient neuroglycopenia to induce seizure, unconsciousness or coma.

Self-monitored plasma glucose values may not be available, but neurological recovery attributable to the restoration of plasma glucose to normal is considered sufficient evidence that the event was induced by a low plasma glucose concentration.

Note: “requiring assistance of another person” means that the patient could not help himself or herself to treat the hypoglycemia. Assisting a patient out of kindness, when assistance is not required, should not be considered a “requires assistance” incident. A severe hypoglycemic incident should be confirmed by the Investigator.

Any hypoglycemic event which leads to unconsciousness, coma, or seizure should also be reported as an SAE.

#### **11.5.1.2 Documented symptomatic hypoglycemia**

Documented symptomatic hypoglycemia is an event during which typical symptoms of hypoglycemia accompanied by a measured plasma glucose concentration of  $\leq 3.9$  mmol/L ( $\leq 70$  mg/dL).

Clinical symptoms that are considered to result from a hypoglycemic episode are eg, increased sweating, nervousness, asthenia/weakness, tremor, dizziness, increased appetite, palpitations, headache, sleep disorder, confusion, seizures, unconsciousness, or coma.

#### **11.5.1.3 Asymptomatic hypoglycemia**

Asymptomatic hypoglycemia is an event not accompanied by typical symptoms of hypoglycemia but with a measured plasma glucose concentration  $\leq 3.9$  mmol/L ( $\leq 70$  mg/dL).

Note: low plasma glucose values without symptoms or signs should not be reported more than once within 30 minutes. Repeated low glucose values within a short period could be due to malfunction of the device, error testing or following up a low glucose reading. The Investigator should try not to document false low SMPG values or redundant low glucose values as asymptomatic hypoglycemic event. Further clarification with the patients is needed.

[figure not shown]
